## **7. Research methods and procedures**

All subjects need to sign informed consent before screening, and successful subjects can enter this study. According to the protocol, the experimental group and the control group were treated respectively, and the effectiveness and safety were evaluated at 1, 2, 3 and 4 weeks. Telephone and video follow-up were conducted 4 weeks after discharge for statistical analysis. Treatment continued until subjects completed the 4-week course or met any of the exit criteria. Participants are evaluated comprehensively by the investigator, and if it is determined that the continuation of the experimental treatment can bring clinical benefit to the subject, the treatment can be continued until the subject's PD, intolerance, or death.

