| statistic analysis  | 
Analysis set
 
Statistical analysis was carried out using full analysis set, coincidence scheme set and security analysis set.
 
Full analysis set (FAS) : Included all randomised participants who had received at least one study intervention and had a measurable baseline stroke.
 
Per Protocol Set (PPS) : In the FAS population, participants with at least one post-intervention awareness scale assessment, good adherence, and no significant violations or deviations from the trial protocol.
 
Safety Set (SS) : defined as subjects who received at least one intervention and were subsequently evaluated for safety.
 
Sample size determination: The sample size is estimated according to
 |

|                           |  |
|---------------------------|--|
|                           | 
the group design of two sample rates compared sample size estimation formula
 $n = \frac{2 \times (U_\alpha + U_\beta)^2 \times P \times (1-P)}{(P_1 - P_2)^2}$ $P = \frac{(P_1 * n_1 + P_2 * n_2)}{(n_1 + n_2)}$ 
Where, <math>U_\alpha</math> is the first type of error probability <math>U</math> value, <math>U_\beta</math> is the second type of error probability, when bilateral <math>\alpha=0.05</math>, unilateral <math>\beta=0.1</math>, <math>U_\alpha=1.96</math>, <math>U_\beta=1.28</math>, <math>P_1</math> is the effective rate of the treatment group, <math>P_2</math> is the effective rate of the control group, and <math>P</math> is the rate of the two combinations. According to previous research literature [1], <math>P_1</math> and <math>P_2</math> are estimated to be 79.4% and 54.8%, resulting in <math>n \approx 76</math>, and the minimum sample size of each group is about 76 cases. As shedding cases were not excluded during the study, the shedding rate was 15%. For the successful completion of the experiment, 87 cases were assigned to each group based on various factors, and 174 cases were required to be included in the two groups.
 
Statistical analysis: All data in the experiment were tested and analyzed for normality, and SPSS 25.0 statistical software was used for analysis and processing.
 |
| follow-up          | Telephone and video follow-up  |

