### Test flow chart

| item                                 | Screening period |                  | Duration of treatment (weeks) |   |   |   | Four weeks after discharge | Quit |
|--------------------------------------|------------------|------------------|-------------------------------|---|---|---|----------------------------|------|
|                                      | 4week s~2days    | base line /-1day | 1                             | 2 | 3 | 4 | Phone or video follow-up   |      |
| Informed consent                     | X                |                  |                               |   |   |   |                            |      |
| Demography                           | X                |                  |                               |   |   |   |                            |      |
| Inclusion/exclusion criteria         | X                |                  |                               |   |   |   |                            |      |
| Medical history                      | X                |                  |                               |   |   |   |                            |      |
| CRS-R scale                          |                  | X                | X                             | X | X | X | X                          |      |
| GCS score                            |                  | X                | X                             | X | X | X | X                          |      |
| NIHSS score                          |                  | X                | X                             | X | X | X | X                          |      |
| FOUR score                           |                  | X                | X                             | X | X | X | X                          |      |
| Electroencephalogram                 |                  | X                |                               |   |   | X |                            |      |
| brainstem auditory evoked potentials |                  | X                |                               |   |   |   | X                          |      |
| encephalofluctuograph                |                  | X                |                               |   |   |   | X                          |      |

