### **(2) Evaluation:**

Consciousness levels were assessed before intervention, at 1, 2, 3, and 4 weeks of treatment, and 4 weeks after discharge: GCS score, NIHSS score, CRS-R Scale (Modified Coma Recovery Scale), and FOUR scale score . Electroencephalogram, brainstem auditory evoked potentials and encephalofluctuograph were examined before intervention and at 4 weeks of treatment.

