## **7.3 follow-up period**

Consciousness level assessment: GCS score, NIHSS score, CRS-R scale, FOUR

scale score.

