8.1.1 Glasgow Coma Scale (GCS) : 3 to 15 points

Open eyes (E) : 1-4 points; Vocalization (V) : 1-5 points; Exercise (M) :1-6 points.

The consciousness improvement rate of each patient was calculated according to the following formula:

Consciousness improvement rate of each patient = (score after treatment - score before treatment)/score before treatment  $\times 100\%$

Consciousness improvement rate  $\geq 20\%$  is effective,  $15\% \leq$  consciousness improvement rate  $< 20\%$  is effective, good consciousness

Turnover rate  $< 15\%$  is invalid

Efficiency = (obvious + effective)/(obvious + effective + ineffective)  $\times 100\%$

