8.1.2 Revised Coma Recovery Scale (CRS-R) : 0-23 points

The minimum state of consciousness (MCS) was assessed as: visual  $> 1$  or auditory  $> 2$  or verbal response  $> 2$  or motor  $> 2$  or communication  $> 0$  or arousal  $> 2$ ;

The evaluation criteria of persistent vegetative state (VS) were: vision  $\leq 1$  score, hearing  $\leq 2$  score, speech response  $\leq 2$  score, movement  $\leq 2$  score, communication = 0 score and arousal  $\leq 2$  score;

Clarity of mind was assessed on a scale of exercise = 6 points or communication = 2 points.

A change from below MCS to MCS, or from MCS to VS, or from VS to clear consciousness, or an increase of one level or more in the state of consciousness is considered valid.

8.2 Safety evaluation: Events such as needle dizziness, hematoma and unstable vital signs were recorded in the case report and reported to the trial designer. After group discussion, the case was withdrawn from the study. Follow-up of subjects after adverse events: in-hospital monitoring, 1 week after discharge, 4 weeks back to the hospital for re-examination.

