### **13.3 Statistical method**

The analysis included case distribution, demographic data, baseline analysis and therapeutic effect analysis. Baseline data included sex, age, stroke type, stroke duration, underlying medical history (diabetes, hypertension, heart disease, chronic obstructive pulmonary disease), and history of smoking and alcohol use. Baseline data were tested by chi-square test. The end point data was the score of the State of Consciousness scale, and the measurement data was expressed as mean SD. Univariate analysis of variance was used to compare the difference between groups at the same time point, the difference at different time points in the group, and the difference before and after between the two groups.  $P < 0.05$  was considered statistically significant, and multiple comparisons were performed by Dunnett-t test.

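### The scales at 4 weeks after discharge may be scored by telephone, where GCS eye and motor items and much of the CRS-R cannot be observed, and the plan does not separate these scores from the in-hospital ones

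*Combined protocol and SAP*

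**What the plan says.** **Mode.** The follow-up row of the Summary of research scheme reads "Telephone and video follow-up", and Section 7 uses the same pairing: "Telephone and video follow-up were conducted 4 weeks after discharge for statistical analysis". The Test flow chart heads the column for 4 weeks after discharge "Phone or video follow-up" and marks GCS, CRS-R, NIHSS and FOUR in it.

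**Scales.** Section 7.3 repeats the list for the follow-up period: "Consciousness level assessment: GCS score, NIHSS score, CRS-R scale, FOUR". Section 7.2 (2) places the visit in one sequence with the others: "Consciousness levels were assessed before intervention, at 1, 2, 3, and 4 weeks of treatment, and 4 weeks after discharge: GCS score, NIHSS score".

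**Analysis.** Section 13.3 applies analysis of variance between groups at the same time point and to "the difference at different time points in the group". Section 13.4 repeats this. Neither section treats remotely obtained scores differently.

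**Not stated.** The plan does not say when telephone and when video is used, who applies the stimuli at the patient's side, or how an item the evaluator cannot see is scored or set to missing. The reliability and validity statement in Section 1.1.3.1 concerns the Chinese CRS-R and its manual. It does not mention remote use.

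**The concern.** These scales rate what a trained evaluator sees and elicits: eye opening, movement, visual pursuit, arousal. Over a telephone most of that is out of reach, and an evaluator who must still enter a score has to leave items blank, guess, or rely on what someone at the bedside reports.

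Follow-up is the only scheduled assessment after discharge, so it is the plan's only evidence on whether any effect lasts. If the way of scoring changes at exactly that visit, a rise or fall since week 4 cannot be attributed to the patient. With no field for mode, the reader of the results could not tell how many scores are affected or in which arm.

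**Working it through.** **Inputs.** GCS components from Section 8.1.1: "Open eyes (E) : 1-4 points; Vocalization (V) : 1-5 points; Exercise (M) :1-6 points". CRS-R subscale maxima from Section 1.1.3.1: auditory 4, visual 5, motor 6, speech 3, communication 2, arousal 3.

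**Step 1: reproduce the stated totals.**
- GCS minimum 1 + 1 + 1 = 3; maximum 4 + 5 + 6 = 15. This matches the stated 3 to 15, leaving 15 − 3 = 12 points above the floor.
- CRS-R maximum 4 + 5 + 6 + 3 + 2 + 3 = 23. This matches the stated 0 to 23.

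**Step 2: GCS by voice only.** Only the verbal item can be heard. Eye and motor items contribute (4 − 1) + (6 − 1) = 8 of 12 points above the floor, or 67%.

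**Step 3: CRS-R by voice only.** The documents do not say which subscales can be judged by voice, so this is an assumption and the range is shown.

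| Subscales judged by voice | Points not observable | Share of 23 |
|---|---|---|
| Speech only | 23 − 3 = 20 | 87% |
| Speech, communication | 23 − 5 = 18 | 78% |
| Speech, communication, auditory | 23 − 9 = 14 | 61% |
| Speech, communication, auditory, arousal | 23 − 12 = 11 | 48% |

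The third row (visual 5 + motor 6 + arousal 3 = 14) is the working figure. Only the most generous reading, which credits both auditory and arousal items to voice, falls just below half.

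**Step 4: CRS-R categories.** Section 8.1.2 requires all six subscales to lie at or below their limits for VS. Two of them, visual and motor, are unobservable in every row above, so voice alone cannot establish VS. Clear consciousness, defined by motor 6 or communication 2, could be shown only through communication.

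**Step 5: which comparisons are touched.**
- *Within group, week 4 to follow-up:* the observed change is the change in the patient plus the change due to method. Nothing in the data would separate the two.
- *Between groups at follow-up:* both arms are scored remotely, so modes are not mixed across visits, but each score carries added error.
- *Week 4 and earlier:* these scores are not obtained remotely, so they are untouched.

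That the earlier scores are bedside ratings is inferred from inpatient treatment (Summary, study design; Section 9.3.3). That follow-up scores are analysed with them is inferred from Sections 7, 7.2 and 13.3 read together. No single sentence states either, and none contradicts them.

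**The case against.** The best defence is that the Summary and Section 7 join telephone and video with *and*. If every follow-up assessment includes video, eye opening and movement can be seen and the voice-only arithmetic does not apply. That is a fair reading, but the flow chart says *or*, and the documents do not settle it. Even by video, someone at the bedside must apply the stimuli, and the plan names nobody.

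It is also fair that the point counts measure what cannot be observed. They do not estimate bias in any comparison. Section 13.3 lists no time points, and both arms follow the same follow-up plan, so the expected harm between groups is added error. The documents give no mechanism that would make it differ by arm.

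Four stronger readings are tempting, and the documents do not support them:

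- *That the primary result is compromised.* Section 3 names no time point for GCS, but Section 8.1 ties effectiveness to before and after the intervention and week 4. The follow-up contact is not listed there.
- *That telephone scores are unblinded family reports.* Section 4.2.2 says families and scale evaluators are both unaware of the grouping, and nothing says that a family report replaces the evaluator's rating.
- *That mode depends on the patient's course, because patients with adverse events come "4 weeks back to the hospital for re-examination".* Section 8.2 does not say the scales are scored at that visit, and it describes such cases as withdrawn from the study.
- *That a one-point remote error changes responder status at particular baseline GCS values.* The responder rule in Section 8.1.1 uses the score after treatment and is not applied to the follow-up contact. Its sensitivity to one point comes from the definition, whatever the mode.

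**Conclusion.** The concern holds for the follow-up visit. As written, the plan allows telephone-only scoring of scales whose items largely have to be seen: 67% of the GCS range above the floor and, on the working assumption, 61% of CRS-R points (48% to 87% across assumptions). The within-group comparison of week 4 with follow-up would then be uninterpretable as patient change, and the between-group follow-up comparison would be noisier by an amount the documents do not allow one to estimate.

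This rests on three things: telephone alone being permitted, as in the flow chart; the in-hospital scores being bedside ratings; and the follow-up scores entering the Section 13.3 comparisons. The week-4 result stands apart from this problem. The point should be corrected, but it does not undermine the trial's main comparison as Section 8.1 describes it.

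**What to change.** 1. Reconcile the Summary, the Test flow chart and Section 7 on the mode of follow-up.
2. In Section 7.3, score the four scales remotely only by video, with a caregiver carrying out the evaluator's instructions. Use telephone contact for survival and safety only. State that items that cannot be observed are recorded as missing.
3. Add a CRF field for the mode of each follow-up assessment.
4. In Section 3, name the bedside week-4 GCS as the primary time point, consistent with Section 8.1.
5. In Sections 13.3 and 13.4, exclude remote follow-up scores from the within-group time-point ANOVA. Report the between-group follow-up comparison separately, as secondary or exploratory.
6. Show mode by arm descriptively only. Mode is determined after randomisation, so treatment effects split by mode would not be protected by it.

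**Cost.** Protocol and SAP wording and one CRF field, with no added visits. The real downside is more missing follow-up scores where video is unavailable; their number should be reported by arm. Under Section 13.2 a patient without a follow-up score can still belong to the full analysis set, which requires only one effectiveness evaluation.

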## Summary of research scheme

|                            |  |
|----------------------------|--|
| scheme name         | Study on the effect of Tongyuan acupuncture on consciousness disorder after stroke   |
| applicant           | Nanfang Hospital, Southern Medical University  |
| major investigators |  |
| research center     | Department of Rehabilitation, Nanfang Hospital, Southern Medical University  |
| research object     | Stroke patients with conscious disturbance   |
| purpose of research | Objective: To investigate whether Tongyuan acupuncture can improve the consciousness disorder after stroke
Secondary objective: To investigate the possible mechanism of action   |
| Research grouping   | Trial group: Tong Yuan acupuncture, once a day, 5 days a week for 4 consecutive weeks.Twenty days in total.
Control group: pseudoacupoint method, once a day, 5 days a week for 4 consecutive weeks.Twenty days in total.   |
| study design        | This study was a randomized, placebo-controlled, single-blind study. Patients with post-stroke consciousness disorder hospitalized in the rehabilitation Department of Southern Hospital were randomly included into the experimental group and the control group, and the experimental group was treated with Tongyuan acupuncture on the basis of routine rehabilitation treatment and drug treatment. The control group was treated with 1cm acupuncture at the same depth beside the selected points of the experimental group. Before intervention, treatment for 1 week, treatment for 2 weeks, treatment for 3 weeks, and treatment for 4 weeks (after completion), follow-up:GCS score, CRS-R scale (Modified Coma Recovery Scale) were performed 4 weeks after discharge to assess the conscious state of the patients, and EEG, brainstem evoked potential and brain fluctuation map were examined before intervention and 4 weeks after treatment. The baseline data of the experimental group and the control group showed no statistical difference through statistical analysis. Conventional rehabilitation treatment and drug treatment were adopted by the current guidelines, and the distribution of cases in the two groups was also random. |
| Study duration      | 2023.1.1-2025.12.31  |
| sample size         | 174  |

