## **4.experiment design**

This clinical study was a randomized (1:1), single-blind, single-center, parallel

controlled clinical study. Seventy-two patients were recruited. After signing the informed consent, patients meeting the inclusion/exclusion criteria will be randomly assigned to the experimental group (Tongyuan acupuncture) and the control group (fake acupoint method) in a 1:1 ratio, and a total of 72 patients will be recruited.

Subjects randomized to the trial group will be treated with regular rehabilitation therapy and drug therapy + acupuncture once a day, 5 days a week for 4 weeks. Twenty days in total.

Subjects randomized to the control group will be treated with regular rehabilitation and drug therapy + pseudoacupoint method once a day, 5 days a week for 4 weeks. Twenty days in total.

Safety and study compliance were assessed for each subject at 1, 2, and 3 weeks of initial treatment and at the end of the intervention, and treatment guidance was given by the investigator. A safety assessment and survival follow-up were conducted 4 weeks after discharge, and the corresponding consciousness scale was evaluated.

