## **7.2 therapeutic session**

### **(1) Treatment plan:**

Test group: Subjects will use conventional rehabilitation therapy (exercise training, physical factor therapy, etc.) and drug therapy (such as controlling blood pressure, blood sugar, promoting microcirculation, nutritional nerve and other supportive treatment) + Tongyuan acupuncture method: point selection: Baihui, Zhongwan, Guanyuan, Qihai, Tianshu (double); Point selection criteria: the national standard "Name and Location of points" (GB/T12346-2006). Intervention time: once a day, 5 days a week for 4 consecutive weeks. Twenty days in total.

Control group: Subjects will receive conventional rehabilitation treatment (exercise training, physical factor therapy, etc.) and drug treatment (such as symptomatic support treatment for controlling blood pressure, blood sugar, promoting microcirculation, nutritional nerve, etc.) + pseudacupoint method (acupuncture treatment is performed 1cm apart from the selected points of the experimental group), once a day, 5 days a week, for 4 consecutive weeks. Twenty days in total.

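### Section 7 lets treatment run past the fixed 20-session course with no cap; if used before the visit 4 weeks after discharge, the scores analysed there would compare unequal numbers of sessions

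*Combined protocol and SAP*

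**What the plan says.** The course is fixed in three places for both arms. The Summary of research scheme gives it for the control arm as "Control group: pseudoacupoint method, once a day, 5 days a week for 4 consecutive weeks.Twenty days in total", with the same schedule for the trial arm. Section 4 repeats it for both arms, for the control group as "regular rehabilitation and drug therapy + pseudoacupoint method once a day, 5 days a week for 4 weeks. Twenty days in total". Section 7.2 (1) does so again, for the test group as "once a day, 5 days a week for 4 consecutive weeks. Twenty days in total". Section 6.3 states the schedule for the experimental group only.

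Section 7 first agrees with this: "Treatment continued until subjects completed the 4-week course or met any of the exit criteria". It then allows an exception, "if it is determined that the continuation of the experimental treatment can bring clinical benefit to the subject", in which case "the treatment can be continued until the subject's PD, intolerance, or death".

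The same section says of the later visit: "Telephone and video follow-up were conducted 4 weeks after discharge for statistical analysis". The Test flow chart and Sections 7.2 (2) and 7.3 list GCS, CRS-R, NIHSS and FOUR at that visit. Section 13.3 plans analysis of variance between the groups at each time point.

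**The concern.** Two consecutive sentences of Section 7 give different stopping rules. The first yields the same planned dose in both arms. The second hands the decision to the investigator after randomisation, on a judgement of benefit, without an objective criterion, a ceiling on sessions or a rule for each arm.

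At stake is the only assessment taken after the treatment period. If some patients went on being needled before it, a difference between the arms could come from the randomised technique, from extra sessions, or from the selection of who received them. Planned dose would no longer be equal by design, and the plan contains no analysis rule for separating these sources.

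**Working it through.** The point turns on the text, so the check is which rule governs which assessment.

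1. **Planned dose.** 5 sessions a week × 4 weeks = 20 sessions. This matches the twenty days stated for each arm in the Summary, Section 4 and Section 7.2 (1).

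2. **Stopping rule.** The first rule in Section 7 stops at the end of the course or at an exit criterion. The second stops at PD, intolerance or death. PD is not in the list of abbreviations and is not defined elsewhere. No order of precedence is given. Because the second sentence follows the first directly, it reads as an exception to it.

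3. **Assessments before any continuation.** Baseline and weeks 1, 2, 3 and 4. The Summary treats week 4 as the end of the course ("treatment for 4 weeks (after completion"), and Section 8.1 places the GCS effectiveness evaluation before and after the intervention and at 4 weeks. These scores are taken before extra sessions could start.

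4. **Assessments after possible continuation.** The visit 4 weeks after discharge. It is timed from discharge, not from session 20, so continued needling can fall before it.

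5. **Whether another rule closes the gap.**
   - Section 6.4 (3) ends observation when the family turns to other treatments during the treatment period. Continued study acupuncture is not another treatment.
   - Section 6.5 requires detailed recording of drugs, not of acupuncture.
   - The per-protocol set in Section 13.2 removes serious protocol violations. Continuation that Section 7 permits is not a violation, so these patients would stay in.
   - The Test flow chart shows no treatment after week 4, but it does not forbid any.

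6. **Which arm.** The sentence speaks of continuing the experimental treatment. Sections 4 and 6.3 use the label experimental for the Tongyuan group, so the sentence may apply to that arm only. It may also mean study treatment in either arm. The text does not settle this.

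7. **Size.** Let discharge fall d weeks after session 20; d is an assumption, since no discharge date is given. At 5 sessions a week, needling in hospital leaves room for at most 5 × d extra sessions: 0 for d = 0, 10 for d = 2, 20 for d = 4. This bounds opportunity only. Turning it into GCS or CRS-R points would need the share of patients continuing in each arm and the effect of an added session, and the documents give neither. The direction is also open. Extra true needling could widen a difference, extra sham contact could narrow it, and a longer stay would move the visit itself.

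**The case against.** The strongest reply is that this is a stray sentence and not a design decision. The 20-day course is stated repeatedly, no part of the plan schedules or analyses an extension, and Section 7.1 asks for a history of HCC, which points to text carried over from another protocol. Staff may never act on it. All of that is fair, and it is why the consequence is stated conditionally. What remains is that the sentence is operative in the current text and staff could follow it as written.

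A second reply is that no objective or endpoint concerns persistence of effect, and that follow-up timed from discharge gives a varying interval since session 20 in any case. This stands: deleting the sentence will not make the visit a clean measure of durability. But the visit is collected for analysis and the groups are compared there, so equal planned dose still matters.

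Three stronger readings are tempting and are not supported:

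- *Dose could double or more by follow-up.* This needs needling at the full rate after discharge. No section describes outpatient sessions; the patients are inpatients (Section 9.3.3) and the later visit is by telephone or video. With needling in hospital only and discharge straight after session 20, there are no extra sessions.
- *Nobody would know who had more.* The case report form is not among the documents, Section 4 assesses compliance up to the end of the intervention, and Section 14.3.2 requires complete recording in general terms. The supportable statement is that the protocol does not explicitly require sessions beyond 20 to be recorded.
- *The effective rate in Section 8.1.1 is at risk because its post-treatment score carries no date.* That is a separate matter. Section 8.1 and the Summary point to week 4, which is unaffected.

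**Conclusion.** The contradiction is real and worth removing. It is limited to the visit 4 weeks after discharge, and it has an effect only if the continuation sentence is followed before that visit; the documents do not say whether it will be. In that case the GCS and CRS-R comparisons there would involve unequal numbers of sessions, selected after randomisation on perceived benefit and possibly in one arm only. No size or direction of bias can be derived from the documents.

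A reader might infer that the main efficacy result is compromised because GCS is the primary endpoint. The documents do not support that: the week-4 GCS evaluation precedes any continuation. Nor is continuation literally without end, since three stopping conditions are named. What is missing is a limit on sessions or weeks and a usable meaning for PD.

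**What to change.** Delete the continuation sentence from Section 7. State in its place that study needling, true or sham, stops at session 20 in both arms and that none is given before the follow-up assessment. Add one case report form item, completed in both arms, for any acupuncture received between session 20 and follow-up, with number of sessions and dates.

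The cost is one deleted sentence, one added statement and one form item. Sample size and the visit schedule do not change. The small downside is that a patient thought to be benefiting waits until after follow-up for further study acupuncture.
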